## 12. DATA REPORTING / REGULATORY REQUIREMENTS

Adverse event lists, guidelines, and instructions for AE reporting can be found in Section 7.0 (Adverse Events: List and Reporting Requirements).

### 12.1 Data Reporting

#### 12.1.1 Method

The Office of Data Quality (ODQ) will collect, manage, and perform quality checks on the data for this study.

#### 12.1.2 Responsibility for Data Submission

Investigative sites are responsible for submitting data and/or data forms to the Office of Data Quality in accordance with DF/HCC SOPs.

### 12.2 Data Safety Monitoring

---

CONFIDENTIAL

This document is confidential. Do not disclose or use except as authorized.

The DF/HCC Data and Safety Monitoring Committee (DSMC) will review and monitor toxicity and accrual data from this study. The committee is composed of medical oncologists, research nurses, pharmacists and biostatisticians with direct experience in cancer clinical research. Information that raises any questions about participant safety will be addressed with the Overall PI and study team.

The DSMC will review each protocol up to four times a year or more often if required to review toxicity and accrual data. Information to be provided to the committee may include: up-to-date participant accrual; current dose level information; DLT information; all grade 2 or higher unexpected adverse events that have been reported; summary of all deaths occurring within 30 days of intervention for Phase I or II protocols; for gene therapy protocols, summary of all deaths while being treated and during active follow-up; any response information; audit results, and a summary provided by the study team. Other information (e.g. scans, laboratory values) will be provided upon request.

### **12.3 Multicenter Guidelines**

This protocol will adhere to the policies and requirements of the DF/HCC Multi-Center Data and Safety Monitoring Plan. The specific responsibilities of the Overall PI, Coordinating Center, and Participating Institutions and the procedures for auditing are presented in Appendix B.

- The Overall PI/Coordinating Center is responsible for distributing all IND Action Letters or Safety Reports to all participating institutions for submission to their individual IRBs for action as required.
- Mechanisms will be in place to ensure quality assurance, protocol compliance, and adverse event reporting at each site.
- Except in very unusual circumstances, each participating institution will order the study agent(s) directly from supplier. A participating site may order the agent(s) only after the initial IRB approval for the site has been forwarded to the Coordinating Center.

## **13. STATISTICAL CONSIDERATIONS**

The primary endpoint of this phase I study is to determine the recommended phase 2 dose (RP2D) of ivosidenib in patients with *IDH1*-mutant myeloid neoplasms after allogeneic HSCT. Each cohort of patients will be treated starting somewhere between days 30 and 90 after HSCT. Dose-limiting toxicities (DLTs), as defined in section 5, will be assessed within the first cycle of treatment (1 cycle = 28 days).

Two doses of ivosidenib will be considered: 250mg daily (dose level 1), and 500mg daily (dose level 2). Dose level 2 is the starting dose level.

A 3+3 design will be used. A cohort of 3 evaluable patients will be treated at each dose level. Patients will be considered unevaluable for the determination of RP2D if they never start

---

CONFIDENTIAL

This document is confidential. Do not disclose or use except as authorized.

ivosidenib maintenance therapy, drop out or die within 28 days of starting treatment without developing DLT for reasons unrelated to therapy. Only patients who start ivosidenib but are unevaluable for DLT can be replaced, to ensure 3 or 6 patients are evaluable for DLT per dose level. Proportion of patients who consent but never start ivosidenib, and proportion of patients who are replaced, will be monitored and reported. All patients who receive any amount of ivosidenib will be evaluated for toxicity.

RP2D will be determined according to the rules described in the Table below.

Number of observed DLTs at a Given Dose Level	Decision Rule
0/3	3 additional evaluable patients will be treated at the dose level. If $\leq 1$ of the 6 treated patients experience a DLT, this is the RP2D. If $\geq 2$ of the 6 treated patients experience a DLT and current dose is dose level 2, de-escalate to dose level 1.
$\geq 2$	De-escalate to dose level 1 if current dose is dose level 2.
1/3	Add 3 more patients at current dose level  c) If 0 of these 3 additional patients experience DLT, current dose is RP2D.  d) If $\geq 1$ of these 3 additional patients experience DLT, then de-escalate to dose level 1 if current dose is dose level 2.
$\leq 1/6$	Current dose is the RP2D

\*Note: If  $\geq 2/3$  or  $\geq 2/6$  DLTs are observed at dose level 1 (250mg daily), the trial will be discontinued.

Once the RP2D is established, an additional 10 patients will be treated at the RP2D to provide a better estimate of the toxicity of ivosidenib. With 16 evaluable patients treated on the RP2D, the 90% confidence interval of the toxicity rate will be within  $\pm 22\%$ . The RP2D defined in this study will then be used to plan a larger phase II study.

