**Treatment may not begin without confirmation from the Coordinating Center that the participant has been registered.**

### **5. TREATMENT PLAN**

#### **5.1 Treatment Regimen**

Ivosidenib will be administered orally every day for 28 consecutive days, defined as a treatment cycle. Appropriate dose modifications are described in Section 6. Reported adverse events and potential risks are described in Section 7. No investigational or commercial agents or therapies other than those described below may be administered with the intent to treat the participant's myeloid malignancy.

---

CONFIDENTIAL

This document is confidential. Do not disclose or use except as authorized.

The starting dose of ivosidenib (AG-120) will be 500mg orally daily. After 3 (or 6) participants are treated at 500mg daily, if this dose is tolerated, then an additional 10 participants will be treated at 500mg daily. If the 500mg daily dose is NOT tolerated in the initial cohort of participants, then the dose will be decreased to 250mg daily. If 250mg daily is tolerated, then an additional 10 participants will be treated at 250mg daily. The only doses studied will be 500mg daily and 250mg daily (the latter, if necessary).

The first cohort will consist of three participants. After the third participant is enrolled to the cohort, enrollment will be put on hold until all three participants have completed the first 28-day cycle. The period for dose-limiting toxicity (DLT) evaluation is the first 28-day cycle. Individual participants must receive at least 50% of the dosing to be DLT evaluable for that cohort. If this criteria is not met, the patient in that dose-escalation cohort may be replaced.

If one of three participants in a cohort experiences a DLT, then an additional 3 participants will be observed at that dose. The recommended phase 2 dose (RP2D) is defined as the highest dose level at which 0 or 1 of six participants experiences a dose-limiting toxicity.

Dose Escalation Schedule	
Dose Level	Dose of Ivosidenib
Level 1	250mg daily
Level 2 – Starting Dose	500mg daily

Once the RP2D is defined, an additional 10 participants will be enrolled at that dose.

If 250mg daily dosing is not tolerated, then the study will end without expansion.

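### No prespecified rule links DLTs in the 10-patient expansion to continued accrual or to the RP2D

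*Combined protocol and SAP*

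**What the plan says.** Section 5.1 defines the RP2D as the "highest dose level at which 0 or 1 of six participants experiences a dose-limiting toxicity". The decision tables in Sections 5.4 and 13 apply that rule, and every row has a denominator of 3 or 6. So does the note to the Section 13 table: if at least 2 of 3 or 2 of 6 "DLTs are observed at dose level 1 (250mg daily), the trial will be discontinued".

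The expansion follows with no condition attached. Section 5.1: "Once the RP2D is defined, an additional 10 participants will be enrolled at that dose". Section 13: "Once the RP2D is established, an additional 10 patients will be treated at the RP2D to provide a better estimate" of the toxicity rate. On precision it adds "With 16 evaluable patients treated on the RP2D, the 90% confidence interval of the toxicity rate will be within" ±22%, and then: "The RP2D defined in this study will then be used to plan a larger phase II study".

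The enrolment hold in Section 5.1 is written for the first three-patient cohort. Section 5.4 assesses DLTs in cycle 1 and does not confine this to the first six patients; later-cycle toxicity is monitored but not counted as DLT.

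On oversight, Section 12.2 says "The DSMC will review each protocol up to four times a year". The same sentence allows more frequent review if needed, DLT information is among the items that may be supplied, and safety questions go to the overall principal investigator and study team. Appendix B, Section 3.2, says that closures and temporary holds take effect at once. Neither place gives a DLT count or refers to the RP2D.

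**The concern.** Section 13 makes the RP2D the primary endpoint. Six patients say little about a DLT rate: after 1 of 6, the exact 90% confidence interval runs from 0.9% to 58.2%. The expansion supplies 10 of the 16 observations at the chosen dose, yet the plan attaches no decision to them.

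An example shows the inconsistency. The plan rejects 2 of 6 (33%). If 1 of 6 is followed by 5 of 10, the total is 6 of 16 = 37.5% (exact 90% interval 17.8% to 60.9%), a higher observed rate on more patients. No written rule then pauses accrual or reopens the RP2D. At stake are participants enrolled at a dose that the plan's own proportion would reject, and a phase II dose whose standing is settled by judgement after the data are seen.

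**Working it through.** **1. The plan's own figure.** For n = 16 the widest exact (Clopper-Pearson) 90% interval is at 8/16, with half-width 0.221. The normal approximation gives 1.645 × √(0.25/16) = 0.206. The stated ±22% reproduces as a half-width. The gap is that no decision rests on it.

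**2. Inputs.** Pass rule: at most 1 DLT in 6 (Sections 5.1, 5.4, 13). Expansion: 10, so 16 at the RP2D (Section 13). Accrual: 1 to 2 a month (Section 13, Sample Size), so the expansion takes 10/2 = 5 to 10/1 = 10 months. True DLT rate p: not in the documents; 10% to 50% is assumed as a range.

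**3. Chance of passing on six.** With q = 1 − p, P(pass) = q⁶ + 6pq⁵.
- p = 1/3: 0.0878 + 0.2634 = 0.351
- p = 0.40: 0.0467 + 0.1866 = 0.233
- p = 0.50: 0.0156 + 0.0938 = 0.109

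Expected DLTs in the expansion are 10p: 3.3, 4 and 5. The chance of at least 4 in 10 is 62% at p = 0.40 and 83% at p = 0.50.

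**4. What a boundary at the plan's own proportion would do.** Hold when cumulative DLTs at the RP2D reach n/3, rounded up: 3 by patients 8-9, 4 by 10-12, 5 by 13-15. Start from the distribution of 0 or 1 DLT in six given passing, add one patient at a time from n = 7 to 16, and remove the probability that reaches the boundary.

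At p = 0.40, 0 and 1 DLT have conditional probabilities 0.2 and 0.8.
- n = 8: 0.8 × 0.4² = 0.1280
- n = 9: two DLTs at n = 8 has probability 0.2 × 0.4² + 0.8 × 2 × 0.4 × 0.6 = 0.416; times 0.4 gives 0.1664
- n = 11, 12, 14, 15, by the same step: 0.0645, 0.0940, 0.0403, 0.0618
- Sum: 0.555

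| True DLT rate | P(pass) | P(hold given pass) | Mean expansion patients treated |
|---|---|---|---|
| 10% | 88.6% | 1.7% | 9.9 |
| 15% | 77.7% | 5.3% | 9.7 |
| 20% | 65.5% | 11.5% | 9.4 |
| one third | 35.1% | 39.2% | 7.9 |
| 40% | 23.3% | 55.5% | 7.0 |
| 50% | 10.9% | 77.0% | 5.6 |

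The last column assumes that accrual does not resume after a hold. With no rule, all 10 are treated at every rate unless someone intervenes.

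**5. Entries that cannot be reached.** One patient at a time, 3 of 7 is impossible after at most 1 of 6. Passing n = 15 means at most 4 DLTs, so n = 16 has at most 5. A count of 6 or more of 16 therefore matters only if results arrive in batches.

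**The case against.** A reader might infer that the RP2D cannot be revised, or must go to phase II whatever the expansion shows. The documents do not say that. They give the expansion a purpose and a precision, say that the RP2D will be used to plan phase II, and nowhere forbid a change. Section 5.1 even foresees the whole study being reduced to 250 mg while some participants remain on 500 mg, although the only written trigger for that is the 3- and 6-patient table. The expansion also serves the second primary objective in Section 1.2, safety and tolerability, so its data are not idle.

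A reader might also infer that only one or two DSMC reviews could fall within the expansion. That assumes the fastest accrual and quarterly review. At 1 a month there is time for about three, and Section 12.2 allows more. Expedited reporting (Section 7.4), immediate reporting of life-threatening toxicity (Appendix B, Section 3.9) and monthly site teleconferences (Appendix B, Section 5.1) add further oversight. All of this stands, and it narrows the point to the absence of a prespecified rule. It does not remove it, because none of these routes carries a DLT threshold or a consequence for the RP2D.

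The boundary has limits too. At a true rate of one third it misses about 61% of the doses that passed. Over all trials, pass-then-hold occurs in 0.351 × 0.392 = 14%, 0.233 × 0.555 = 13% and 0.109 × 0.770 = 8% at the three high rates. Extending the 2-of-6 proportion to 16 patients is a choice, since no unacceptable rate is stated. Section 2.3 reports no maximum tolerated dose up to 1200 mg a day, but outside the post-transplant maintenance setting that this trial exists to study.

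**Conclusion.** The point holds as an omission. Section 13 has no prespecified rule by which DLTs in the expansion affect accrual or the RP2D, and the safeguards after patient six are discretionary. It does not show that the sponsor or the DSMC would be unable or unwilling to act, and the ±22% statement is not in error.

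Doses with a true DLT rate of one third to 50% reach the expansion with probability 35% to 11%. A boundary at one third would hold 39% to 77% of those, and cut the mean number treated in the expansion from 10 to between 7.9 and 5.6. These figures rest on assumed true rates, independent patients with a common rate, and each 28-day result being known before the next patient is counted. It is a cheap improvement, not a fault that invalidates the design.

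**What to change.** Add a short paragraph and table to Section 13 stating that:
- cycle 1 DLTs in the expansion are counted cumulatively with those of the first six evaluable participants at the RP2D;
- accrual is held for DSMC review when the count reaches one third of evaluable participants: 3 by 8-9, 4 by 10-12, 5 by 13-15, with 6 or more of 16 applying only when results arrive in batches;
- participants whose 28-day result is pending are handled in a stated way, for example whether accrual waits for them (at 2 a month about two would be pending);
- if the boundary is crossed, the RP2D is reported as not confirmed, and any further dose evaluation needs a protocol amendment.

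The last item keeps the stated maximum of 22. Without it, a crossing at one level followed by a full evaluation and expansion at the other could reach 16 + 16 = 32. The rule concerns accrual and reporting only; it sets no dose and no management of individual participants. The sponsor may choose a similar boundary, provided it is written down beforehand with its operating characteristics.

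The cost is the text itself and a small chance of an unnecessary hold: 1.7%, 5.3% and 11.5% at true rates of 10%, 15% and 20%, given passing. No patients are added.

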## SCHEMA

If only three participants were enrolled at the RP2D level, then an additional 3 participants will be enrolled to confirm that  $\leq 1$  out of 6 participants experiences a DLT at this dose.

If two out of three (or two out of six) participants at 250 mg daily have a DLT, then this dose will be considered to be too toxic in this population.

---

CONFIDENTIAL

This document is confidential. Do not disclose or use except as authorized.

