#### **5.4 Definition of Dose-Limiting Toxicity (DLT)**

Dose-limiting toxicities will be evaluated during cycle 1 (first 28 days) of treatment. Toxicities will be graded and documented according to NCI CTCAE version 4.03.

Non-hematologic DLTs will be defined as any drug-related grade 3 or greater event.

The following exceptions will NOT be considered DLTs in this population:

- grade 3 nausea, vomiting, or diarrhea that lasts  $\leq$  72 hours and responds to medical intervention

Hematologic DLTs will be defined as any drug-related grade 4 neutropenia ( $ANC < 500/\mu L$ ) or thrombocytopenia (platelets  $< 25,000/\mu L$ ) that

- has not resolved to grade 1 or less within 14 days of holding ivosidenib, or
- resolves within 14 days, but then recurs after resuming study drug

Note that anemia is not included as a DLT.

Additionally, febrile neutropenia of any duration, and not due or attributable to the underlying disease or other extraneous causes such as infection, will be considered a DLT.

In addition, any  $\geq$  grade 2 non-hematologic toxicity that the participant finds intolerable or renders the participant unable to take 75% of the assigned doses (e.g. multiple dose interruptions) during the first cycle will be considered a DLT.

Management and dose modifications associated with the above events are outlined in Section 6.

Dosing will proceed within each cohort according to the following scheme.

Number of observed DLTs at a Given Dose Level	Decision Rule
0/3	3 additional evaluable patients will be treated at the dose level. If $\leq 1$ of the 6 treated patients experience a DLT, this is the RP2D. If $\geq 2$ of the 6 treated patients experience a DLT and current dose is dose level 2, de-escalate to dose level 1.
$\geq 2$	De-escalate to dose level 1 if current dose is dose level 2.

CONFIDENTIAL

This document is confidential. Do not disclose or use except as authorized.

1/3	Add 3 more patients at current dose level  a) If 0 of these 3 additional patients experience DLT, current dose is RP2D.  b) If $\geq 1$ of these 3 additional patients experience DLT, then de-escalate to dose level 1 if current dose is dose level 2.
$\leq 1/6$	Current dose is the RP2D

Subsequent (after cycle 1) cycles of ivosidenib will continue, with participants monitored for toxicity and adverse event reporting, but will not be used for DLT evaluation.

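### The 16-patient toxicity estimate at the RP2D pools six patients admitted only with 0 or 1 DLT, so given selection it is biased low, and the ten unselected patients are not shown separately

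*Combined protocol and SAP*

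**What the plan says.** A dose qualifies by its DLT count. Section 5.1 says that the RP2D "is defined as the highest dose level at which 0 or 1 of six participants experiences a dose-limiting toxicity". The decision tables in Sections 5.4 and 13 apply the same rule, and the Schema ensures that six patients are always reached: "If only three participants were enrolled at the RP2D level, then an additional 3 participants will be enrolled to confirm that" at most one of six has a DLT. Section 5.4 fixes the window: "Dose-limiting toxicities will be evaluated during cycle 1 (first 28 days) of treatment".

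Once the dose is chosen, Section 13 says that "an additional 10 patients will be treated at the RP2D to provide a better estimate of the toxicity of ivosidenib", and gives the precision for both groups together: "With 16 evaluable patients treated on the RP2D, the 90% confidence interval of the toxicity rate will be within" ±22%. It adds: "The RP2D defined in this study will then be used to plan a larger phase II study".

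Section 13 does not mention that the first six were selected on their DLT count. No section plans a separate result for the ten expansion patients. The term used for the rate is not defined, and the interval method is not named.

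**The concern.** The ordinary binomial interval assumes that all 16 patients are a sample whose outcomes did not decide whether they were counted. For 6 of the 16 (37.5%) that is untrue. Their observed DLT rate cannot exceed 1/6, whatever the true rate, because with two or more DLTs the dose would not have become the RP2D. Pooling them with the ten unselected patients pulls the estimate down.

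The error is on the unsafe side, because toxicity looks lower than it is. The expansion exists to give a better toxicity estimate for a dose that goes forward to phase II planning. The distortion grows with the true rate, so it is largest when a fairly toxic dose has passed by chance, which is when a better estimate is most needed.

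**Working it through.** **Inputs.** Six dose-finding patients at the RP2D, kept only with 0 or 1 DLT (Schema, Sections 5.1, 5.4 and 13). Ten expansion patients and a 90% level (Section 13), taken as two-sided because it is given as ±. The true cycle 1 DLT rate p is not in the documents, so a range is assumed. The toxicity rate is read as the cycle 1 DLT rate, because Section 13 ties evaluability to DLT ("to ensure 3 or 6 patients are evaluable for DLT per dose level").

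**The plan's own figure.** The exact (Clopper-Pearson) 90% interval is widest at 8/16: 27.9% to 72.1%, half-width 22.1 points. The ±22% is reproduced for 16 unselected patients.

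**Bias given selection.** Let X be the DLTs in the first six, Y ~ Binomial(10, p) those in the expansion, and T = X + Y.

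- Chance that the dose passes: P(X ≤ 1) = (1−p)^6 + 6p(1−p)^5.
- E[X | X ≤ 1] = 6p(1−p)^5 / P(X ≤ 1) = 6p/(1+5p).
- Bias of T/16 = [6p/(1+5p) + 10p]/16 − p = −15p²/[8(1+5p)].
- At p = 0.30: −15 × 0.09 / (8 × 2.5) = −0.0675.

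**Interval given selection.** The exact n = 16 limits were summed over the distribution of T given X ≤ 1. An upper-limit miss means that the upper limit lies below the true rate (nominal 5%).

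| True rate | Dose passes | Bias (points) | Coverage given selection | Upper-limit miss given selection | Dose passes and upper limit misses |
|---|---|---|---|---|---|
| 10% | 89% | −1.3 | 99.4% | 0% | 0% |
| 20% | 66% | −3.8 | 95.3% | 4.3% | 2.8% |
| 30% | 42% | −6.8 | 93.7% | 6.2% | 2.6% |
| 35% | 32% | −8.4 | 87.2% | 12.8% | 4.1% |
| 40% | 23% | −10.0 | 92.9% | 7.1% | 1.6% |
| 50% | 10.9% | −13.4 | 79.9% | 20.1% | 2.2% |

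For 16 unselected patients the upper-limit miss would be 2.8%, 2.6%, 4.5%, 1.8% and 3.8% at 20%, 30%, 35%, 40% and 50%.

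On a grid of true rates from 1% to 50% in steps of 0.1 point, coverage given selection is at least 92% up to a true rate of 25%. Between 25% and 40% it falls below 90% only at 26.4–26.6% and 34.4–37.1%, with a minimum of 86.3%. The joint probability in the last column never exceeds 5.0%.

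**The ten alone.** Their rate is unbiased. On the same grid the exact 90% interval has an upper-limit miss of at most 5.0% and coverage of at least 92.3%. The cost is width: the maximum half-width is 27.8 points, at 5/10.

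**Example, 4 DLTs in 16.** The pooled rate is 25.0% (9.0–48.4%). If the split is 1/6 and 3/10, the ten give 30.0% (8.7–60.7%). If it is 0/6 and 4/10, they give 40.0% (15.0–69.6%). Given selection and T = 4, the first split has probability 6·C(10,3)/[C(10,4) + 6·C(10,3)] = 720/930 = 77%, and the second 23%. The estimate conditional on selection is (4 − 0.774)/10 = 32.3% (11.2–62.0%).

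**The case against.** The strongest points on the other side are these.

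- **The rate is undefined.** Section 13 speaks of toxicity, not DLT, and also says "All patients who receive any amount of ivosidenib will be evaluated for toxicity". If a broader rate is meant, the bias depends on its correlation with cycle 1 DLT, which the documents do not give. This stands as a limit on the figures. It is also a reason to define the rate.
- **No decision is tied to the pooled rate.** No threshold depends on it, and it is the dose that is carried into phase II planning. This limits the consequence. It does not remove a downward bias from the estimate that the expansion is meant to improve.
- **The pooled rate is the more precise figure.** This is correct. Root mean squared error given selection, at true rates of 10/20/30/40%, is 0.068/0.093/0.116/0.141 pooled and 0.095/0.126/0.145/0.155 for the ten alone. The order reverses only near 50% (0.168 against 0.158), where the dose rarely passes. The pooled rate should therefore stay the main figure.
- **Trial-wide error is controlled.** It is, at 5.0% or less. But a 16-patient estimate exists only if a dose was selected, so its reader faces the conditional error.
- **The split can be recovered.** The RP2D decision implies the first-six count, and the ten follow by subtraction if DLTs are reported for all 16. The plan does not commit to either.

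**Conclusion.** The concern holds. Given selection, the planned pooled rate understates the cycle 1 DLT rate by about 1 point at a true rate of 10% and by about 4 to 10 points at 20% to 40%. The interval errs mostly by having its upper limit too low. The half-width itself is correctly calculated. What is missing is any statement that it leaves the selection out, and any separate view of the ten unselected patients. The size rests on three assumptions: that the rate means cycle 1 DLT, that the true rate lies in the assumed range, and that patients' outcomes are independent with a common rate. The design stands. This should be corrected in the analysis text because it is cheap and the bias is on the unsafe side.

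**What to change.** In Section 13:

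1. Keep the pooled 16-patient rate as the main figure, label it the cycle 1 DLT rate, name the interval method, and state that ±22% does not account for the requirement of at most 1 DLT in the first six.
2. Beside it, report DLTs separately for the first six and the ten expansion patients, with an exact 90% interval for the ten (half-width up to 28 points).
3. Optional: add an estimate and exact 90% interval conditional on selection. A conditionally unbiased estimate is (T − q)/10, with q = 6·C(10, T−1)/[C(10, T) + 6·C(10, T−1)]. Its root mean squared error at 10/20/30/40% is 0.085/0.118/0.139/0.150.

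Items 1 and 2 cost one sentence and one table row, with no added patients, visits or data. The drawback is that the added figures are less precise than the pooled rate at true rates of 10–40%, so they supplement it and do not replace it. Whether DLTs in the expansion bear on the RP2D is a separate matter for the sponsor and the DSMC; nothing is proposed on it here.
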